#### 6.1.8.2 Preparation and Administration

VARIVAX® is supplied as a lyophilized vaccine to be reconstituted using the accompanying sterile diluent. See the VARIVAX® package inset (45).

The procedures for administering the product are the same as those described in [Section 6.1.1.2](#).

Each 0.5 mL dose is to be injected SC into the outer aspect of the upper arm as indicated in the Operating Guidelines [Section 5.1.4](#).

#### 6.1.8.3 Dose Selection and Timing

Subjects in Group 1 will receive VARIVAX® at 12 to 15 months of age. Subjects in Group 2 will receive VARIVAX® at 12 months of age.

#### 6.1.9 Identity of Other Product 7

**HAVRIX®:** (Hepatitis A Vaccine) (GlaxoSmithKline Biologicals 411 Rixensart, Belgium)

**Form:** Suspension for injection

**Dose:** 0.5 mL

**Route:** IM

**Batch number:** TBD

#### 6.1.9.1 Composition

Each 0.5 mL pediatric dose of vaccine contains 720 enzyme-linked immunosorbent assay (ELISA) Units (EL.U.) of viral antigen, adsorbed onto 0.25 mg of aluminum as aluminum hydroxide.

Excipients:

Amino acid supplement in a phosphate-buffered saline solution supplement	.....0.3% weight/volume
Polysorbate 20 .....	0.05 mg/mL
Residual MRC-5 cellular proteins .....	not more than 5 µg/mL
Formalin .....	not more than 0.1 mg/mL
Neomycin sulfate.....	not more than 40 nanograms/mL
Aminoglycoside antibiotic.....	included in the cell growth media

#### 6.1.9.2 Preparation and Administration

**HAVRIX®** is supplied as 0.5 mL prefilled syringes. See the **HAVRIX®** package insert (46).

The procedures for administering the product are the same as those described in [Section 6.1.1.2](#).

Each 0.5 mL dose is to be injected IM as indicated in the Operating Guidelines and [Section 5.1.4](#).

#### 6.1.9.3 Dose Selection and Timing

Subjects in Subgroups 1b, 2a, and 2b will receive **HAVRIX®** at 15 to 18 months of age.

### 6.2 Product Logistics

#### 6.2.1 Labeling and Packaging

The investigational product, MenACYW conjugate vaccine (single-dose vials), and control product will be supplied with investigational labeling and packaging according to national regulations. Each single dose of investigational or control product will be identified by a unique number on the on the detachable label and on the outer carton label. The carton label will also have a detachable label for the sites to attach to the source documents. See the Operating Guidelines for additional label detail.

The investigational and control products are blinded.

All of the concomitant products will retain original commercial labeling and packaging with no additional labels to be applied.

The concomitant products (licensed routine vaccines) are not blinded.

## 6.2.2 Product Shipment, Storage, and Accountability

### 6.2.2.1 Product Shipment

The Clinical Logistics Coordinator or designee will contact the Investigator or a designee to determine the dates and times of delivery of products.

Each vaccine shipment will include a temperature-monitoring device to verify maintenance of the cold chain during transit. On delivery of the product to the site, the person in charge of product receipt will follow the instructions given in the Operating Guidelines, including checking that the cold chain was maintained during shipment (i.e., verification of the temperature recorders). If there is an indication that the cold chain was broken, this person should immediately quarantine the product, alert the Sanofi Pasteur representative, and request authorization from Sanofi Pasteur to use the product.

### 6.2.2.2 Product Storage

The Investigator will be personally responsible for product management or will designate a staff member to assume this responsibility.

At the site, products must be kept in a secure place with restricted access. The Study and Control Products (MenACYW conjugate vaccine or MENVEO®) will be stored in a refrigerator at a temperature ranging from +2°C to +8°C and never frozen. All commercially labeled products should be stored according to the manufacturer's instructions. The temperature must be monitored and documented (see the Operating Guidelines) for the entire time that the vaccine is at the study site. In case of accidental freezing or disruption of the cold chain, vaccines must not be administered and must be quarantined, and the Investigator or authorized designee should contact the Sanofi Pasteur representative for further instructions.

### 6.2.2.3 Product Accountability

The person in charge of product management at the site will maintain records of product delivery to the trial site, product inventory at the site, the dose(s) given to each subject, and the disposal of or return to the Sponsor of unused doses.

The necessary information on the product labels is to be entered into the source document and the CRB. If applicable, information may also be entered into the subject's vaccination card.

The Sponsor's monitoring staff will verify the study site's product accountability records against the record of administered doses in the CRBs and the communication from the IRT system (if applicable).

In case of any expected or potential shortage of product during the study, the Investigator or an authorized designee should alert the Sanofi Pasteur representative as soon as possible, so that a shipment of extra doses can be arranged.

### **6.2.3 Replacement Doses**

If a replacement dose is required (e.g., because the syringe broke or particulate matter was observed in the syringe), the site personnel must either contact the IRT system to receive the new dose allocation, or follow the instructions given in the Operating Guidelines.

### **6.2.4 Disposal of Unused Products**

Unused or wasted products will be returned to the Sponsor in accordance with the instructions in the Operating Guidelines. Product accountability will be verified throughout the study period.

### **6.2.5 Recall of Products**

If the Sponsor makes a decision to launch a retrieval procedure, the Investigator(s) will be informed of what needs to be done.

## **6.3 Blinding and Code-breaking Procedures**

Given that the meningococcal vaccines (investigational and control) used in this study have different appearances and preparation methods, and that vaccination schedule in the second year of life differs in the number of vaccines administered and timing of their administration, the study has a partially modified double blind design. The study is conducted modified double blind for the infant part of the study, with everyone involved in the study (participants/parents, investigators, safety outcome assessor, Sponsor) blinded to the meningococcal vaccine received, except the personnel administering the vaccine. An unblinded vaccine administrator will administer the appropriate vaccine but will not be involved in safety data collection. The CRB will be design to ensure that the blind nature of the study will be maintained during the study. However, during the toddler part of the study, individuals blinded during the infant part of the study might be potentially unblinded due to the different timing of and age of the subjects at the vaccination visits, and number of vaccines received during these visits. Conducting the study in this manner will allow the blinded evaluation of safety data to the extent the study design permits in order to avoid bias.

The code may be broken in the event of an AE only when the identification of the vaccine received could influence the treatment of the subject. Code-breaking should be limited to the subject(s) experiencing the AE.

- The blind can be broken by the Investigator or a delegate through the IRT system, as explained in the code-breaking procedures described in the Operating Guidelines. Once the emergency has been addressed by the site, the Investigator or a delegate must notify the Sanofi Pasteur RMO if a subject's code was broken. All contact attempts with the Sponsor prior to unblinding are to be documented in the source documents, and the code breaking CRF is to be completed.

A request for the code to be broken may also be made:

- by the GPV Department through an internal system for reporting to health authorities in the case of an SAE as described in International Conference on Harmonisation (ICH) E2A. In this case, the code will be broken only for the subject(s) in question. The information resulting from code-breaking (i.e., the subject's vaccine or group assignment) will not be communicated to either the Investigator or the immediate team working on the study, except for the GPV representative.

The IEC / IRB must be notified of the code-breaking. All documentation pertaining to the event must be retained in the site's study records and in the Sanofi Pasteur files. Any intentional or unintentional code-breaking must be reported, documented, and explained, and the name of the person who requested it must be provided to the Sponsor.

#### **6.4 Randomization and Allocation Procedures**

On the day of enrollment, subjects who meet the inclusion/exclusion criteria and whose parent / guardian signs the ICF will be randomly assigned to Group 1 or Group 2 in a 2:1 ratio such that Group 1 will have approximately 1752 subjects and Group 2 will have approximately 876 subjects.

Each group will be further randomized 2:1 in 2 subgroups based on the time of analyses conducted in the 2nd year of life (30 days after the 12-month or 30 days after the 15-month vaccination) into 2 subgroups:

Group 1:

Subgroup 1a (G1a) (12 months): MenACYW conjugate vaccine and routine vaccines at 2, 4, 6, and 12 to 15 months of age

Subgroup 1b (G1b) (15 months): MenACYW conjugate vaccine at 2, 4, 6, and 15 to 18 months of age and routine vaccines at 2, 4, 6, 12 to 15 months of age, and 15 to 18 months of age

Group 2:

Subgroup 2a (G2a) (12 months): MENVEO® at 2, 4, 6, and 12 months of age and routine vaccines at 2, 4, 6, 12, and 15 to 18 months of age

Subgroup 2b (G2b) (15 months): MENVEO® at 2, 4, 6, and 12 months of age and routine vaccines at 2, 4, 6, 12, and 15 to 18 months of age

Site staff will connect to the IRT system, enter the identification and security information, and confirm a minimal amount of data in response to IRT system prompts. The IRT system will then provide the vaccine assignment and subject number. The full detailed procedures for group allocation are described in the Operating Guidelines. If the subject is not eligible to participate in the study, then the information will only be recorded on the subject recruitment log.

Subject numbers that are assigned by the IRT system will consist of a 12-digit string (a 3-digit country identifier, a 4-digit study center identifier, and a 5-digit subject identifier). For example, Subject 840000100005 is the fifth subject enrolled in Center Number 1 in the US (840 being the US country code).

Subject numbers should not be reassigned for any reason. The randomization codes will be kept securely in the IRT system.

## 6.5 Treatment Compliance

The following measures will ensure that the vaccine doses administered comply with those planned, and that any non-compliance is documented so that it can be accounted for in the data analyses:

- All vaccinations will be administered by qualified study personnel
- The person in charge of product management at the site will maintain accountability records of product delivery to the study site, product inventory at the site, dose(s) given to each subject, and the disposal of unused or wasted doses

## 6.6 Concomitant Medications and Other Therapies

At the time of enrollment, ongoing medications including but not limited to other therapies (e.g., blood products), should be recorded in the source documents. All new medications prescribed for new medical conditions / AEs during study participation should also be recorded in the source documents.

Documentation in the CRB of concomitant medication(s) will be limited to specific categories of medication(s) (Categories 1, 2, and 3 as detailed below). Those will include Category 1, 2, and 3 medications ongoing at the time of inclusion in the study, or started at any time during the subject's participation in the trial. For category 3 medication, the period of reporting in CRB will be restricted to only 3 days (72 hours) prior to each blood sampling time point.

### Collection period in source documents

Reportable medications (Category 1, 2, and 3) will be collected in the source documents from the day of first vaccination to the end of the trial.a

### Categories of Reportable medications and reporting period

Reportable medications include medications that impact or may impact the consistency of the safety information collected after any vaccination and/or the immune response to vaccination.

- Category 1: Reportable medications with potential impact on the evaluation of the safety of the study vaccines. For example, antipyretics, analgesics, non-steroidal anti-inflammatory drugs (NSAIDs), systemic corticosteroids (therapy duration less than 2 weeks), and other immune modulators. Category 1 medications do not define the Per-Protocol Analysis Set (PPAS).

*Note: Topical steroids (Inhaled, otic, ophthalmic, nasal etc.) should not be captured or reported.*

- Category 1 medications will be reported in the CRB from the day of first vaccination to the end of the solicited and unsolicited follow-up period after each vaccination. These

a Subjects/ Subject's parents will be required to document all medications received in the Diary Cards. The sites will focus on only recording the medications belonging to the 3 categories in the other source documents.

medications will also be collected in the CRB for the 30- day period prior to the subsequent doses of the vaccine, wherever applicable (second, third, fourth, etc., in case of a multi-dose schedule with more than a 30-day interval between doses).

- Category 2: Reportable medications with potential impact on immune response of the study vaccines and used to define the PPAS. For example:

- Flu vaccines administered within 14 days pre or post each trial vaccination, including the day of the study vaccination visit

Any vaccine other than study vaccines (vaccines non-described in the Protocol) within the 28 days (4 weeks) preceding or after the trial vaccination, including the day of the study vaccination visit.

- Immune globulins, blood or blood-derived products: used in the 3 months preceding the first blood draw and up to the last blood draw
- Immunosuppressive therapy such as immune-suppressors, immune-modulators with immunosuppressive properties, long-term systemic corticosteroids therapy (prednisone or equivalent for more than 2 consecutive weeks) within past 3 months, anti-cancer chemotherapy, anti-proliferative drugs such as DNA synthesis inhibitors, or radiation therapy: used in the 6 months preceding the first trial vaccination, and up to the last blood draw.

- Category 2 medications will be reported in the CRB during the study period up to the last blood draw.
- Category 3: Systemic (Oral or injectable) antibiotics, as they may interfere with bioassays used for antibody testing when taken before a blood draw. Antibiotics that the subject received within 72 hours preceding each visit for blood draw related to IMP assessment (meningococcal vaccines) and used to define the PPAS.
- Category 3 medications will be reported in the CRB for the period of 3 days (72 hours) before each blood draw.

*Note: Topical antibiotics (Inhaled, otic, ophthalmic, nasal, etc.) should not be captured or reported.*

The information reported in the CRB for each reported medication will be limited to:

- Trade name
- Rationale for the origin of prescription: Whether it was a prophylactica\* medication? Prophylactic medications will be recorded in the Action Taken section of the AE collection tables.
- Medication category (1, 2, or 3)
- Start and stop dates

Dosage and administration route, homeopathic medication, will not be recorded.

a Medication(s) prescribed for preventing AE occurrence (e.g. paracetamol to reduce the risk of fever)

If the subject has received medications other than those listed in Categories 1, 2, and 3, the detailed information will be collected in the source documents only.

Medications given to treat an AE will be captured in the “Action Taken” section of the AE CRB only. No details will be recorded in the concomitant medication CRB unless the medication(s) received belongs to one of the prelisted categories.

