4.3.2.3.2 Reactogenicity (Solicited Reactions from Day 0 to Day 7 After Each Vaccination)

After the first vaccination, parents / guardians will be provided with a diary card, a digital thermometer, and a flexible ruler, and will be instructed how to use them. The following items will be recorded by the subject's parent / guardian in the diary card on the day of each vaccination and for the next 7 days (i.e., D0 to D07) until resolution:

- Daily temperature, with the route by which it was taken
- Daily measurement or intensity grade of all other solicited injection site and systemic reactions
- Action taken for each event (e.g., medication)

The action(s) taken by the parent or guardian to treat and/or manage any solicited reactions will be classified in the CRB using the following list (all applicable items should be checked):

- None
- Medication
- Health care provider contact

- Hospitalized
- Discontinuation of study vaccination

Parents / guardians will be contacted by telephone 8 days after each vaccination to remind them to record all safety information in the diary card.

If the timing of the telephone call should fall on a weekend or a holiday, the call should be made on the next business day. If contact is not made on the designated day, study staff will continue calling until contact is made. Every telephone attempt and its outcome will be documented in the source document.

Table 4.1 and **Table 4.2** present, respectively, the injection site reactions and systemic reactions that are prelisted in the diary cards and CRB, together with the intensity scales.

Table 4.1: Solicited injection site reactions: terminology, definitions, and intensity scales

CRB term (MedDRA lowest level term [LLT])	Injection site tenderness	Injection site erythema	Injection site swelling
MedDRA preferred term	Injection site pain	Injection site erythema	Injection site swelling
Diary card term	Tenderness	Redness	Swelling
Definition	Pain when the injection site is touched or injected limb mobilized	Presence of a redness including the approximate point of needle entry	Swelling at or near the injection site Swelling or edema is caused by a fluid infiltration in tissue or cavity and, depending on the space available for the fluid to disperse, swelling may be either soft (typically) or firm (less typical) to touch and thus can be best described by looking at the size of the swelling

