4.4.2.5 Other Safety Endpoints

4.4.2.5.1 Action Taken

This information will be summarized as collected, including missing observations. No derivation or imputation will be done.

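### Protocol 6.6 sends preventive medication to the Action Taken field, which is defined elsewhere as treatment or management of an event, and the SAP tabulates that field without separating the two

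*Protocol*

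**What the plan says.** Protocol 6.6, under the categories of reportable medications, lists the items reported in the case report book (CRB) for each medication: trade name, a prophylaxis item ("Rationale for the origin of prescription: Whether it was a prophylactic" medication), category, and start and stop dates. Attached to the prophylaxis item is the instruction "Prophylactic medications will be recorded in the Action Taken section of the AE collection tables". The footnote defines the term: "Medication(s) prescribed for preventing AE occurrence (e.g. paracetamol to reduce the risk of fever"). A little further on, the same section sends treatment to the same place: "Medications given to treat an AE will be captured in the" Action Taken section of the adverse event CRB.

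The field itself is defined in the reactogenicity sections (Protocol 9.3.2.3.2, SAP 4.3.2.3.2): "The action(s) taken by the parent or guardian to treat and/or manage any solicited reactions will be classified in the CRB". Protocol 9.3.2.3.3 and SAP 4.3.2.3.3 say the same for unsolicited events. The list has five options: none, medication, contact with a health care provider, hospitalization, and discontinuation of study vaccination. None is for prophylaxis.

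Action taken is a component of the solicited-reaction, unsolicited-event and medically-attended-event endpoints (Protocol 9.3.2.2, SAP 4.3.2.2) and appears in SAP Table 5.5. SAP 4.4.2.5.1 gives the handling: "This information will be summarized as collected, including missing observations", with no derivation.

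**The concern.** One code is asked to hold two opposite reasons for giving a drug. A child given paracetamol beforehand to prevent fever, who then has a reaction, could be tabulated as having had that reaction treated. A reader of the action-taken table takes the medication line as a rough measure of how troublesome the reactions were, and under Section 6.6 as written it would not be a clean one.

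The protocol itself treats this class of drug as relevant to safety. Category 1 consists of medications that may affect the evaluation of vaccine safety, and its examples begin with the drugs in question: "For example, antipyretics, analgesics, non-steroidal anti-inflammatory drugs (NSAIDs"). At stake is the meaning of a descriptive safety summary.

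**Working it through.** The plan gives no figure to reproduce, so the check sets the rules side by side.

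1. **What Section 6.6 puts into Action Taken.** Prophylactic medication by one sentence, and medication given to treat an event by another.
2. **What the field means.** Treatment or management of a reaction (Protocol 9.3.2.3.2, SAP 4.3.2.3.2) or of an unsolicited event (Protocol 9.3.2.3.3, SAP 4.3.2.3.3). A dose given before any event, to prevent one, does not fit either definition.
3. **Whether the codes can separate them.** No. There is one medication option, and the listed options carry no date and no link to a medication record.
4. **Whether the SAP separates them.** No. SAP 4.4.2.5.1 reports the field as entered. SAP 5.8 says the concomitant-medication category fields were inactivated and the medications coded with WHODrug. It does not say that the prophylactic item was dropped, and it gives no rule for using either source to interpret Action Taken.
5. **Whether prophylaxis is recorded elsewhere.** Yes. Section 6.6 states: "Category 1 medications will be reported in the CRB from the day of first vaccination". That reporting runs to the end of each post-vaccination follow-up and also covers the 30 days before later doses. It does not depend on an event occurring. The footnote to the collection period in Section 6.6 also has parents enter every medication in the diary card. An antipyretic used as treatment is Category 1 too, so both uses reach the concomitant-medication form and the prophylactic item there can tell them apart.

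**Illustration of size, on assumed rates only.** Let t be the share of reactions truly treated, x the share of children given prophylaxis independently of t, and c the share of that prophylaxis entered as medication under Action Taken. The displayed share is t + (1 − t) × x × c. None of t, x or c is in the documents.

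With c = 1 (every prophylactic use entered against the reaction):

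| | x = 5% | x = 15% | x = 30% |
|---|---|---|---|
| t = 20% | 20 + 80 × 0.05 = 24% | 20 + 80 × 0.15 = 32% | 20 + 80 × 0.30 = 44% |
| t = 30% | 30 + 70 × 0.05 = 33.5% | 30 + 70 × 0.15 = 40.5% | 30 + 70 × 0.30 = 51% |

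With c = 0 (sites apply the treat-or-manage definition and ignore the sentence), the displayed share is t and there is no distortion. The table is therefore the top of the range for each pair of assumed rates, not an estimate.

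**The case against.** The strongest reply is that the sentence is a misplaced remark inside a list of concomitant-medication items. Sites filling in Action Taken will follow that field's own definition, and actual entry is governed by the CRB Completion Instructions (Protocol 13.4.1), which are not among the documents. The endpoint is action taken, not reactions needing medication. Safety is descriptive: SAP 5.1.4 tests no hypotheses, and Section 6.6 says Category 1 medication does not define the per-protocol set. All of this stands, and it makes the distortion conditional and its consequence small. It does not remove the contradiction, because the protocol gives sites two incompatible instructions for one field.

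Three stronger readings are tempting, and the documents do not support them.

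- *Prophylaxis in a child without an event goes unrecorded.* The concomitant-medication form and the diary card both record it. What is true is narrower: without an event there is nothing treated for Action Taken to describe, so that field cannot be the sole record. The CRB layout is not shown, and SAP 4.4.2.1.1 implies that prelisted reactions have entries even when marked absent.
- *Treatment of reactions is overstated for both vaccines.* That holds only if sites enter prophylaxis as Section 6.6 directs.
- *Prophylaxis differs between groups and biases the fever comparison.* The protocol concedes possible unblinding in the toddler part (Section 6.3), but nothing indicates differential use. SAP Table 5.5 is a minimum list, so a table of prophylactic use is not excluded, although none is specified.

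**Conclusion.** The point holds as an internal inconsistency of minor weight. Section 6.6 directs preventive medication into a field that both documents otherwise reserve for treating or managing an event, and the SAP reports that field without separating the two. If sites follow Section 6.6, the medication line in the action-taken summaries would mix the two uses and could overstate how often reactions were treated. By how much cannot be derived from the documents. The 24% to 51% shown in the working rests entirely on assumed rates, independence of prophylaxis from treatment, and complete entry of prophylaxis under Action Taken. The effect is confined to descriptive safety tables. No hypothesis, analysis set or power figure changes.

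**What to change.** - **Protocol 6.6:** delete the sentence, or correct it so that prophylactic use is recorded and identified only through the prophylactic item on the concomitant-medication form.
- **SAP 4.4.2.5.1:** state that the medication option under Action Taken means medication given to treat or manage the event.
- **Entries already made:** query them against the prophylactic item and the start and stop dates. This has to be a query. A programmed rule based on dosing after onset cannot be run from the Action Taken codes alone, since they carry no date and the listed medication items include no link to an event.
- **Optional:** one descriptive table of prophylactic antipyretic and analgesic use by group and vaccination visit. Fever with and without prophylaxis is not needed. Prophylaxis is a post-randomization, self-selected factor, so such a split would be descriptive at best.

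The cost is one protocol sentence, one SAP sentence and a round of data queries, plus one table if wanted. No new data collection is required.
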